#### Medical

12. The patient has any other medical disease for which the treatment takes priority over treatment of schizophrenia or is likely to interfere with study treatment or impair treatment compliance.
13. The patient has a moderate or severe ongoing adverse event related to IMP from study 16323A considered of potential safety risk by the investigator.
14. The patient takes or has taken disallowed recent or concomitant medication (specified in [Appendix II](#)) in study 16323A.
15. The patient has a disease or takes medication that could, in the investigator's opinion, interfere with the assessments of safety, tolerability or efficacy, or interfere with the conduct or interpretation of the study.
16. The patient has clinically significant abnormal vital signs considered of potential safety risk by the investigator.
17. The patient has one or more laboratory values outside the reference range, based on the last available blood or urine samples taken during study 16323A that are, in the investigator's opinion, of potential risk to the patient's safety, or the patient has any of the following values at study 16323A (the medical monitor should be contacted in case of uncertainty):
  - a serum creatinine value >1.5 times the upper limit of the reference range
  - a serum total bilirubin value >1.5 times the upper limit of the reference range
  - a serum alanine aminotransferase (ALT) or aspartate aminotransferase (AST) value >2 times the upper limit of the reference range
18. The patient has not previously been diagnosed with diabetes, but meets ANY of the following criteria (newly diagnosed diabetes) based on the last available blood samples taken during study 16323A:
  - HbA1c  $\geq$ 7.0%, OR
  - glucose >6.94 mmol/L (fasting, >125 mg/dL) or >11.1 mmol/L (nonfasting, >200 mg/dL)
  - any other abnormal laboratory tests that in the investigator's clinical judgement are medically significant and would impact on the safety of the patient or the interpretation of the study results.
19. The patient has orthostatic hypotension (defined as a decrease in systolic blood pressure >20 mmHg between two measurements, first in the supine position and then sitting, and standing after the patient has rested in each position for at least 3 minutes).
20. The patient has, based on the last available ECG measurement taken during study 16323A:
  - an abnormal ECG that is, in the investigator's opinion, clinically significant

- a PR interval >250 ms
- a QRS interval >130 ms
- a QTcF interval >450 ms (for men) or >470 ms (for women) (based on the Fridericia correction where  $QTcF = QT/RR^{0.33}$ )
- A patient should also be excluded if he or she has any other abnormal ECG tests that in the investigator's judgment are medically significant and would impact the safety of the patient or the interpretation of the study results.

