Safety and tolerability will be assessed by means of withdrawal, reported adverse events, vitals signs, weight, clinical safety laboratory tests, ECGs, and physical examinations. Metabolic adverse events including body weight gain, dyslipidemia, and hyperglycemia are adverse events associated with antipsychotic treatment and represent an important long-term safety risk. The primary variables for assessing those parameters include body weight/BMI, waist circumference, fasting plasma glucose, glycosylated haemoglobin [HbA1c] and lipids (triglycerides, total cholesterol, low-density lipoprotein [LDL], and high density lipoprotein [HDL] cholesterol).

The long-term efficacy will be explored based on the PANSS a well established scale for assessing severity of the symptoms of schizophrenia. The CGI-S will be used as an additional exploratory efficacy measure of clinical response to treatment. The exploratory assessment of the severity of the negative symptoms of schizophrenia will be done using the NSA-4.

Improvement in functional outcome and quality of life are important treatment goals in the long-term management of patients with schizophrenia. In the current study, effects on functional outcomes will be explored using clinician-reported outcomes such as the PSP, QLS and WoRQ.

Taking into account the substantial health economic burden of schizophrenia, the effect of the Lu AF35700 on subjective well-being, treatment satisfaction, disability and health care resource utilisation will be explored. These will be assessed in the study through patient reported outcomes such as MSQ, Tool and HEA.

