#### Medical

12. The patient has any other medical disease for which the treatment takes priority over treatment of schizophrenia or is likely to interfere with study treatment or impair treatment compliance.
13. The patient has a moderate or severe ongoing adverse event related to IMP from study 16159A considered of potential safety risk by the investigator.
14. The patient takes or has taken disallowed recent or concomitant medication (specified in [Appendix II](#)) in study 16159A.
15. The patient has a disease or takes medication that could, in the investigator’s opinion, interfere with the assessments of safety, tolerability or efficacy, or interfere with the conduct or interpretation of the study.
16. The patient has clinically significant abnormal vital signs considered of potential safety risk by the investigator.
17. The patient has one or more laboratory values outside the reference range, based on the last available blood or urine samples taken during study 16159A that are, in the investigator’s opinion, of potential risk to the patient’s safety, or the patient has any of the following values at study 16159A (the medical monitor should be contacted in case of uncertainty):
  - a serum creatinine value >1.5 times the upper limit of the reference range
  - a serum total bilirubin value >1.5 times the upper limit of the reference range
  - a serum alanine aminotransferase (ALT) or aspartate aminotransferase (AST) value >2 times the upper limit of the reference range
18. The patient has not previously been diagnosed with diabetes, but meets ANY of the following criteria (newly diagnosed diabetes) based on the last available blood samples taken during study 16159A:
  - HbA1C >6.5%, OR
  - fasting plasma glucose >126 mg/dL (7.0 mmol/L), OR
  - non-fasting plasma glucose >200 mg/dL (11.1. mmol).
19. The patient has previously been diagnosed with diabetes, but the condition is unstable as determined by ANY of the following criteria based on the last available blood samples taken during study 16159A:
  - HbA1c ≥7.0%, OR
  - glucose >6.94 mmol/L (fasting, >125 mg/dL) or 11.1 mmol/L (nonfasting, 200 mg/dL)

- any other abnormal laboratory tests that in the investigator’s clinical judgement are medically significant and would impact on the safety of the patient or the interpretation of the study results.

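### 16323A exclusion criterion 18 attaches the known-diabetes limits to patients without a diabetes diagnosis, so no numeric HbA1c or glucose limit covers known diabetes on that entry route

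*Protocol*

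**What the plan says.** Protocol Section 5.3 gives a separate exclusion list for each of three entry routes.

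- **16159A patients.** There are two diabetes criteria. Criterion 18 covers patients without a diagnosis: HbA1c above 6.5%, "fasting plasma glucose >126 mg/dL (7.0 mmol/L), OR" or non-fasting glucose above 200 mg/dL. Criterion 19 covers known disease, with wording that begins "The patient has previously been diagnosed with diabetes, but the condition is unstable as determined by ANY of the following criteria based on the last" and goes on to name the 16159A samples. Its limits are HbA1c at or above 7.0% and "glucose >6.94 mmol/L (fasting, >125 mg/dL) or 11.1 mmol/L (nonfasting, 200 mg/dL"), followed by a general bullet on other abnormal laboratory tests.
- **Other Patients.** There are again two. Criterion 24 repeats the undiagnosed limits. Criterion 25 opens "The patient has previously been diagnosed with diabetes, but the condition is unstable as determined by ANY of the following criteria", uses the 7.0% and 6.94 mmol/L limits, and adds conditions on stable antidiabetic treatment and recent hospitalisation.
- **16323A patients.** There is one. Criterion 18 applies to patients with no earlier diagnosis who meet any of its "criteria (newly diagnosed diabetes) based on the last available blood samples taken during study 16323A". Its bullets are HbA1c at or above 7.0%, "glucose >6.94 mmol/L (fasting, >125 mg/dL) or >11.1 mmol/L (nonfasting, >200 mg/dL"), and the same general laboratory bullet. Criterion 19 is orthostatic hypotension.

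Protocol Section 3.2 describes metabolic events, hyperglycaemia among them, as "adverse events associated with antipsychotic treatment and represent an important long-term safety risk" and names fasting plasma glucose and HbA1c among the primary variables for assessing them.

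**The concern.** The opening of 16323A criterion 18 belongs to one patient group and its limits belong, in the 16159A list, to another. Two things follow if it is applied literally: known diabetes has no criterion of its own on this route, and undiagnosed patients are held to a different HbA1c limit from the one used on the other two routes.

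Literal application is the expected reading, because Protocol Section 14 grants no permission to deviate. The study exists to describe long-term safety and treats glycaemia as one of its main concerns. Entry rules on glycaemia should therefore not differ between routes unless the plan says so and gives a reason. Section 3.2 gives none.

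**Working it through.** There is no sample-size or power figure to reproduce; the Protocol states that no formal calculation was made. The check compares the lists and applies their numeric rules.

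**Step 1. Limits side by side (Protocol Section 5.3).**

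| Group | 16159A | Other Patients | 16323A |
|---|---|---|---|
| Undiagnosed: HbA1c | >6.5% (crit. 18) | >6.5% (crit. 24) | ≥7.0% (crit. 18) |
| Undiagnosed: fasting glucose | >126 mg/dL | >126 mg/dL | >125 mg/dL |
| Known: HbA1c | ≥7.0% (crit. 19) | ≥7.0% (crit. 25) | no criterion |
| Known: fasting glucose | >125 mg/dL | >125 mg/dL | no criterion |

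**Step 2. Units.** Taking 18.016 mg/dL per mmol/L for glucose: 125/18.016 = 6.94, 126/18.016 = 6.99 and 200/18.016 = 11.10 mmol/L. The paired units agree, so the mismatch is not a conversion slip.

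**Step 3. Apply the numeric rules.** They were run over HbA1c from 6.4% to 12.0% and fasting glucose of 110, 126 and 160 mg/dL.

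- *Undiagnosed, HbA1c 6.6% or 6.9%, fasting glucose 110 mg/dL:* excluded by 16159A and Other Patients, not by 16323A. The gap is HbA1c above 6.5% and below 7.0% with fasting glucose at or below 125 mg/dL.
- *Undiagnosed, HbA1c 6.4% or 6.5%, fasting glucose 126 mg/dL:* excluded by 16323A only. On fasting glucose this list is stricter by 1 mg/dL.
- *Known diabetes, HbA1c 7.0%, 8.0% or 12.0% at any of the three glucose values, or fasting glucose 126 or 160 mg/dL at any HbA1c:* excluded by 16159A and Other Patients. No numeric limit applies in 16323A.

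**Step 4. Slip or choice?** The three bullets of 16323A criterion 18 follow 16159A criterion 19 in order and nearly in wording, including the general laboratory bullet. The 16323A list has 20 exclusion criteria and the 16159A list has 21. Both facts fit the loss of one set of limits and one opening line when the list was adapted, but they do not prove it.

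**Step 5. Reach.** Planned: 30/400 = 7.5% (Protocol Section 17.11). Enrolled: 4 (SAP Section 5) out of more than 500 (SAP Section 16), so below 4/500 = 0.8%. SAP Section 5 shows these 4 only in listings.

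**The case against.** The strongest reply is that little turns on this. Several parts of it stand.

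- **Judgement remains.** A reader might infer that a known diabetic from 16323A cannot be excluded at any HbA1c. The documents do not support that. Criterion 17 allows exclusion for any out-of-range laboratory value the investigator considers a risk, with the medical monitor available in doubtful cases; criteria 4, 12 and 15 also apply. What is missing is a numeric limit.
- **The undiagnosed gap is narrow.** A reader might infer that such patients pass up to and including 7.0%. They do not: 7.0% itself is excluded, the glucose limits must also be met, and the fasting limit is slightly stricter here than on the other routes.
- **The lead-in study is unseen.** The entry criteria of 16323A are not in the documents. If that study barred known diabetics, the missing criterion would matter less and could be deliberate. The HbA1c mismatch for undiagnosed patients would remain.
- **Few patients are involved.** With 4 enrolled and none in summary tables, no estimate can move.

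A reader might also see a contradiction within the other two lists, because known diabetics have the looser HbA1c limit but the tighter fasting glucose limit. That is not one: the glucose limits differ by 1 mg/dL, they apply to different groups, and nothing in the Protocol requires the two measures to be ordered alike.

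None of this explains why one list joins the opening of one criterion to the limits of another.

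**Conclusion.** The inconsistency is in the text and changes who is eligible when criterion 18 is followed as written. On the 16323A route, known diabetes is left to investigator judgement with no HbA1c or glucose limit, and undiagnosed patients in the band defined in Step 3 are not excluded by criterion 18 although the other two lists would exclude them.

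The consequence is limited to eligibility safeguards for a small group. It would be tempting to conclude that patients did enter with glycaemic values barred elsewhere; the documents do not show this, and the number affected is unknown. The finding rests on the wording of Section 5.3 alone. Its practical weight depends on 16323A's own entry rules.

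**What to change.** Reconcile 16323A criterion 18 with 16159A criteria 18 and 19 and Other Patients criteria 24 and 25. The revised text should state which patients criterion 18 covers, whether and how known diabetes is covered, and which limits apply to each group. If a difference between routes is intended, give the reason. No view is taken here on which limits are right.

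In the same edit, move the general bullet on other abnormal laboratory tests out of the diabetes criterion. It sits under criterion 18 in the 16323A list and under criterion 19 in the 16159A list, so the change applies to both.

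The cost is amendment wording in Section 5.3. The criterion already relies on existing lead-in blood samples, so no new data are needed. The downside is that a few fewer 16323A patients might be eligible.

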**For patients who can potentially benefit from treatment with Lu AF35700**

General

1. The patient has previously been enrolled in this study.
2. The patient has participated in a clinical study <30 days prior to the Screening Visit.
3. The patient is a member of the study personnel or of their immediate families, or is a subordinate (or immediate family member of a subordinate) to any of the study personnel.
4. The patient is under forced treatment.
5. The patient is pregnant or breast-feeding.
6. The patient has a history of severe drug allergy or hypersensitivity, or known hypersensitivity to any of the IMP(s) or its/their excipients.
7. The patient has a disease or takes medication that could, in the investigator's opinion, interfere with the assessments of safety, tolerability, or efficacy, or interfere with the conduct or interpretation of the study.
8. The patient takes or has taken disallowed recent or concomitant medication (specified in [Appendix II](#)) or it is anticipated that the patient will require treatment with at least one of the disallowed concomitant medications during the study.
9. The patient is, in the investigator's opinion, unlikely to comply with the protocol or is unsuitable for any reason.

Psychiatric

10. The patient has any current psychiatric disorder (DSM-5™ criteria) other than schizophrenia established as the primary diagnosis.
11. The patient suffers from intellectual disability, organic mental disorders, or mental disorders due to a general medical condition (DSM-5™ criteria).
12. The patient is experiencing acute exacerbation of his/her psychotic symptoms at the Screening Visit, between the Screening and Baseline Visits or at the Baseline Visit according to the investigator's judgment.
13. The patient is treated with clozapine at the time of the Screening Visit.
14. The patient has a current diagnosis or a history of substance use disorder according to DSM-5™ criteria within 6 months prior to the Screening Visit with the exception of tobacco, or mild cannabis or mild alcohol use disorder. Patients with a positive drug screen test with the exception of cannabis and verified by repeated testing are excluded from the study.

15. The patient is at significant risk of harming himself/herself or others according to the investigator's clinical judgement, or who on the C-SSRS:
  - Answers "Yes" to questions 4 or 5 on the Suicidal Ideation section within the last 3 months at Screening, OR
  - Answers "Yes" to any question on the Suicidal Behaviour section within the last 3 months at Screening, OR
  - Answers "Yes" to questions 4 or 5 on the on the Suicidal Ideation section at Baseline.
16. The patient has had neuroleptic malignant syndrome.
17. The patient has started formal cognitive or behavioural therapy or systematic psychotherapy within 6 weeks prior to Screening, or plans to start such therapy during the study. Any ongoing formal psychotherapy initiated more than 6 weeks prior to Screening should be continued with the same methodology and at the same frequency and intensity during the entire study.

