- The Safety Follow-up Visit will be done 6 weeks (+3 days) after the last dose of IMP. This visit can be a telephone contact, unless an SAE has occurred since last visit or unless there was a clinically significant abnormal safety laboratory test value at the last visit. In such cases, safety follow-up(s) must be scheduled to allow for a medical examination and/or blood sampling. Further Safety Follow-up Visits beyond 6 weeks may be needed as judged by the

- investigator (if further Safety Follow-up Visits are performed, these must be recorded in the patient's medical record, and not in the CRF).
- e. If the date of a patient visit does not conform to the study plan, subsequent visits should be planned to maintain the visit schedule relative to the Baseline Visit. The number of days between 2 visits should not exceed the number of days for which the patient has been dispensed IMP.
  - f. For *16159A-patients* and *16323A-patients*, the data will be linked respectively from the Screening Visit in the study 16159A eCRF or from the Screening Visit in the study 16323A eCRF, when applicable.
  - g. For *16159A-patients* and *16323A-patients*, results from effectiveness/safety assessments and blood/urine samples performed respectively at the Primary Outcome Visit (Visit 12) in study 16159A or at the last day of the dosing period (Day 42) in study 16323A (when available) will be linked to the Baseline Visit (Visit 1) in study 16159B, when applicable.
  - h. For *16159A-patients*, HEA data will be linked from the Baseline A Visit in the study 16159A eCRF.
  - i. To be performed only for newly recruited patients not previously participating in a study investigating Lu F35700.
  - j. Exploratory gene expression profiling (RNA) and metabolomics/proteomics are covered by the main Patient Information Sheet.
  - k. Sampling for pharmacogenetics is optional and a separate Patient Information Sheet covers this analysis. This sampling should preferably be at the Baseline Visit, but may be collected at any visit that includes a clinical safety laboratory sample.
  - l. For *16159A-patients* and *16323A-patients*, ongoing adverse events from study 16159A and 16323A, respectively, are to be transferred by the investigator to the eCRF, when applicable.
  - m. Only for adverse events ongoing at the Primary Outcome/Withdrawal Visit and new SAEs.
  - n. Only to be taken if the laboratory test was clinically significantly abnormal at the Primary Outcome/Withdrawal Visit.

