  - o. Prolactin results will remain blinded throughout the study.
  - p. For *16159A-patients*, additional ECGs will be done; 1 ECG recording before the daily dose is switched to weekly dosing (preferably on the day the decision of switching from daily to weekly dosing is taken) and 1 ECG recording the day after the first weekly dose is taken.
  - q. The first dose of IMP should be taken after the Baseline Visit is completed. All treatment assignment and subsequent IMP assignment is done via the IVRS/IWRS. The IVRS/IWRS will be assessed at the unscheduled visit only if the dose adjustment requires dispensing of IMP.
  - r. The dose of IMP can be increased for efficacy or decreased for tolerability at scheduled or unscheduled visits from Week 1 Visit.
  - s. For *16159A-patients* and *16323A-patients*, ongoing concomitant medication in study 16159A and 16323A, respectively, must be transferred by the investigators to the 16159B eCRF. All prescription, non-prescription medications, and herbal medications taken during study 16159B will be recorded as concomitant medications.
  - t. Urine drug screen tests can be repeated any time during the study at the discretion of the investigator.
  - u. S-βhCG pregnancy test should be performed at the Screening Visit (Only for *Other-patients*), Visit 5, Visit 10 and the Primary Outcome/Withdrawal Visit for women of childbearing potential. Urine pregnancy tests can be performed at any time during the study at the discretion of the investigator.

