- have been surgically sterilised prior to the Primary Outcome Visit in study 16159A.

The following assessments from the Primary Outcome Visit in study 16159A will be linked to the Baseline Visit: PANSS, CGI-S, PSP, NSA-4, QLS, TooL, MSQ, WorQ, HEA, ongoing adverse events, physical examination, waist circumference, weight, vital signs, 12-lead ECG, mSAS, AIMS, BARS, C-SSRS, ongoing concomitant medication, clinical safety laboratory data (including S-βhCG pregnancy test, HBA1c, blood lipid profile) (see [Panel 2](#)).

Additionally, diagnosis, demographics, relevant medical, psychiatric and social history and height will be linked from the Screening Visit in study 16159A to Baseline Visit in this study.

*For patients who completed the dosing period of study 16323A*

Patients who meet each of the inclusion criteria and none of the exclusion criteria at the Baseline Visit (unless otherwise specified; some criteria assessed as part of the last visit of the dosing period in study 16323A) are eligible to participate in this study.

1. The patient has completed the dosing period of study 16323A.
2. The patient is still capable of communicating with the site personnel.
3. The patient and if applicable his or her legal representative is/are able to read and understand the *Informed Consent Form*.
4. The patient and if applicable his or her legal representative has/have signed the *Informed Consent Form* for study 16159B.
5. The patient is willing and able to attend study appointments within the specified time windows.
6. The patient can potentially benefit from 52-week treatment with Lu AF35700 according to the investigator's clinical judgment.
7. The patient has a caregiver or an identified responsible person considered reliable by the investigator (for example, family member, social worker, case worker, or nurse) considered reliable by the investigator in providing support to the patient to ensure compliance with study treatment, outpatient visits, and protocol procedures.
8. The patient has a stable living environment, as demonstrated by the ability to provide contact information for themselves and/or family/friend(s)/caregiver(s).
9. The patient, if a woman, must:
  - agree not to try to become pregnant during the study, AND

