#### Psychiatric

5. The patient has been diagnosed with a primary psychiatric disorder other than schizophrenia during study 16159A.
6. The patient has a clinically significant unstable illness diagnosed during study 16159A.
7. The patient is experiencing an acute exacerbation of his/her psychotic symptoms according to the investigator's clinical judgement.
8. The patient has a current diagnosis of substance use disorder according to DSM 5™ criteria during study 16159A with the exception of tobacco, or mild cannabis or mild alcohol use disorder. Patients with a positive drug screen test at the Baseline Visit, with the exception of cannabis and verified by repeated testing, are excluded from the study.
9. The patient, in the opinion of the investigator, is at significant risk of suicide, or the patient:

- Answers “Yes” to any question on the Suicidal Behaviour section of the C-SSRS, OR
  - Answers “Yes” to questions 4 and 5 on the Suicidal Ideation section of the C-SSRS.
10. The patient has started formal cognitive or behavioural therapy or systematic psychotherapy during study 16159A. Any ongoing formal psychotherapy initiated more than 6 weeks prior to Screening Visit of study 16 159A should be continued with the same methodology and at the same frequency and intensity during the entire study.
  11. The patient has experienced neuroleptic malignant syndrome during study 16159A.

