**For patients who completed study 16159A (*16159A-patients*)**

The Baseline Visit will take place at the same visit as the Visit 12 (Primary Outcome Visit, end of Week 16) of the study 16159A.

After the baseline assessment, for eligible patients, the treatment with Lu AF35700 will be initiated at daily dose of 10 mg at Day 1 of study 16159B. In addition, for *16159A-patients*, the treatment (Lu AF35700, risperidone or olanzapine) received during study 16159A will be tapered down in a blinded fashion with wallets from study 16159A and will be completed in 7 days according to the following scheme:

- Patients randomised to Risperidone: 4 mg/day for the first 3 days; 2 mg/day for the 4 subsequent days, encapsulated tablets, orally, once daily
- Patients randomised to Olanzapine: 10 mg/day for the first 3 days; 5 mg/day for the 4 subsequent days, encapsulated tablets, orally, once daily
- Patients randomised to Lu AF35700: Placebo for 7 days, encapsulated tablets, orally, once daily.

At the end of the first week (Week 1 Visit), all patients will be treated with 10 mg/day Lu AF35700 only.

From the Week 1 Visit, according to the investigator's clinical judgment, the 10 mg/day dose can be increased to 20 mg/day based on the patient's response. Thereafter, the 20 mg/day dose can be reduced to 10 mg/day based on the patient's tolerability to treatment. This can occur at scheduled or unscheduled visits.

From the Week 8 Visit, the switch from Lu AF35700 daily dosing regimen to Lu AF35700 weekly dosing regimen can be performed at any consecutive visit according to the investigator's clinical judgment. The first weekly tablet will be taken 7 days after the last daily tablet. The Lu AF35700 weekly dosing regimen can be switched back to a daily dosing regimen of 10 mg/day for tolerability reasons or to 20 mg/day for worsening of the patient's clinical status. This can occur at scheduled or unscheduled visits. The first daily tablet will be taken 7 days after the last weekly tablet.

The number of patients under weekly dosing regimen will be limited to 50 patients by IVRS/IWRS.

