## **8.3 Baseline Visit (Visit 2)**

Patients previously participating in a study investigating Lu AF35700 will enter in this study directly at the baseline visit. The investigator's evaluation of the patient's eligibility in this study will be done based on the latest data available in the previous LuAF35700 study.

After the baseline visit, the current antipsychotic or study treatment will be tapered down and completed in 7 days.

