**Panel 4 Clinical Safety Laboratory Tests**

Haematology	Livera	Kidneya
B-haemoglobin	S-total bilirubin	S-creatinine
B-erythrocyte count	S-conjugated bilirubin	S-urea nitrogen (BUN)
B-haematocrit	S-alkaline phosphatase (AP)	S-uric acid
B-MCV	S-alanine aminotransferase (ALT)	Urine (dipstick)
B-MCHC	S-aspartate aminotransferase (AST)	U-protein (dipstick)
B-total leucocyte count	S-lactate dehydrogenase (LDH)	U-glucose (dipstick)
B-neutrophils (% of total leucocytes)	S-γ-glutamyl transferase (γGT)	U-blood (dipstick)
B-eosinophils (% of total leucocytes)	Electrolytesa	U-ketones (dipstick)
B-basophils (% of total leucocytes)	S-sodium	Urine drug screenc
B-lymphocytes (% of total leucocytes)	S-potassium	U-Amphetamine
B-monocytes (% of total leucocytes)	S-chloride	U-Barbiturates
B-thrombocyte count	S-bicarbonate	U-Benzodiazepines
P-INR (prothrombin ratio)	S-calcium (total)	U-Cannabinoids
Lipidsa	Endocrine and Metabolica	U-Cocaine
S-cholesterol (total) (fasting)	S-albumin	U-Methadone
S-triglycerides (fasting)	P-glucose (fasting)	U-Opiates
S-low density lipoprotein (LDL)	S-prolactin b	U-Phencyclidine
S-high density lipoprotein (HDL)	B-HbA1c (fasting)	Pregnancy (women only)
	S-total protein	S-hCG
		Urine dipstick d
		Additional Test
		S-Creatine phosphokinase (CPK) e

B – blood; P – plasma; S – serum; U – urine

- Clinical chemistry
- Result will remain blinded
- Urine samples will be collected and analysed at the site using dipsticks
- Can be repeated at any time during the study at the discretion of the investigator. All positive urine pregnancy test results must be confirmed by a serum test.
- S-troponin T, reflex for CPK >500U/l.

Blood samples for the clinical safety laboratory tests will be collected as outlined in [Panel 2](#). The blood sampling and handling procedures are described in the study-specific *Laboratory Specification Manual*.

The blood samples will be analysed at the central laboratory.

The investigator must review (initial and date) the results of the clinical safety laboratory tests as soon as possible after receipt of those results. Out-of-range values must be interpreted by the investigator as “not clinically significant” or “clinically significant” with a comment concerning the planned follow-up. Tests for clinically significant out-of-range values must be

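### The two roll-over exclusion lists do not exclude pregnant or breast-feeding women, and no rule requires a negative pregnancy result before a roll-over woman's first dose

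*Protocol*

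**What the plan says.** Protocol section 5.3 has three separate exclusion lists. The one for Other Patients states as criterion 5: "The patient is pregnant or breast-feeding". The lists for 16159A-patients (criteria 1 to 21) and 16323A-patients (criteria 1 to 20) have no counterpart.

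Roll-over women do have a pregnancy test on file. Section 5.3 includes among the 16159A data linked to Baseline the "clinical safety laboratory data (including S-βhCG pregnancy test, HBA1c, blood lipid profile". Panel 2 marks a Baseline pregnancy test with footnote g, which links "results from effectiveness/safety assessments and blood/urine samples performed respectively at the Primary Outcome Visit (Visit 12) in study 16159A", or those from the last dosing day of 16323A, where available. Footnote u, which lists the serum pregnancy tests, names a pre-dose test only for Other Patients (at Screening). It then names Visit 5, Visit 10 and the final visit. Urine tests are left to the investigator.

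On timing, section 6.1 says for 16159A-patients: "The Baseline Visit will take place at the same visit as the Visit 12". Section 9.5.2 adds: "The blood samples will be analysed at the central laboratory". Section 8.3 says that the eligibility evaluation of roll-over patients "will be done based on the latest data available in the previous LuAF35700 study". The only condition on starting treatment is Panel 2, footnote q: "The first dose of IMP should be taken after the Baseline Visit is completed".

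**The concern.** Section 5.4 requires withdrawal from treatment when a patient becomes pregnant, so the sponsor regards pregnancy as incompatible with Lu AF35700. An entry rule should match that, and for one of the three sources it does. For the other two, a test is linked but its result decides nothing.

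The same roll-over lists do attach consequences to other results. Exclusion 8 in both deals with "Patients with a positive drug screen test at the Baseline Visit", and fixed limits are set for creatinine, bilirubin, ALT/AST, HbA1c, glucose, PR, QRS and QTcF. The linked pregnancy test is the one without a rule.

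At stake is avoidable foetal exposure. It would not end promptly on stopping, because section 1.1.5.2 estimates half-lives of 143 hours for the parent compound and 250 hours for the metabolite.

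**Working it through.** The plan states no figure on this point, so the check is a comparison of the texts with some simple counts.

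**1. The three exclusion lists (section 5.3)**

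| List | Criteria | Naming pregnancy or breast-feeding | Planned patients |
|---|---|---|---|
| 16159A-patients | 21 | 0 | 270 |
| 16323A-patients | 20 | 0 | 30 |
| Other Patients | 28 | 1 (criterion 5) | 100 |

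Roll-over criteria: 21 + 20 = 41, of which 0 mention either condition. Planned entry through the lists without the exclusion: 270 + 30 = 300, and 300 / 400 = 75%.

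**2. Actual enrolment (SAP sections 5 and 16).** No Other Patients were enrolled, more than 500 patients were included, and only 4 came from 16323A. The one list with the exclusion therefore applied to nobody, and the 16159A list governed nearly all entries.

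**3. Could another rule do the same job before the first dose?**

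- Inclusion 9 (both roll-over groups) asks for agreement not to try to conceive, together with contraception, or for postmenopausal or sterilised status. It looks forward; a woman unknowingly pregnant at Baseline can meet it.
- Exclusion 17 depends on the investigator's opinion that an out-of-range laboratory value endangers the patient. It sets limits for creatinine, bilirubin and ALT/AST but does not name pregnancy.
- Exclusion 4 is a general unsuitability clause, again a matter of judgement.
- Section 5.4 acts after entry.
- Footnotes g and u link or schedule tests and state no required result.

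Rules requiring a known negative result before a roll-over woman's first dose: 0.

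**4. Timing.** For both roll-over groups Baseline falls on the same day as the final lead-in dosing visit, which is when the linked sample is taken. Blood goes to a central laboratory, and treatment starts on Day 1 once the visit is complete. Turnaround is not stated, so it is an inference that the serum result may be outstanding at the first dose. The missing rule does not depend on this inference: a result already in hand has no stated consequence either.

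**5. Length of exposure if the Baseline result is not acted on.** The next scheduled test is Visit 5, Day 28 with a window of ±3 days: 28 + 3 = Day 31 at the latest. The half-lives are 143 / 24 ≈ 6.0 days (parent) and 250 / 24 ≈ 10.4 days (metabolite), so exposure continues for some time after stopping.

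**The case against.** The strongest reply is that several safeguards would have to fail together. Women must use highly effective contraception or be unable to conceive. Section 9.5.2 has the investigator review laboratory results as soon as possible after receipt. Section 5.4 would hardly be read as letting a woman found pregnant at Baseline stay on treatment. A site that knew of a positive result would very probably not dose. This stands as far as it goes: Day 31 is a worst case, and the likelier exposure is the laboratory turnaround, which the documents do not give.

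Results pending at dosing are also not peculiar to pregnancy. Other laboratory limits rely on the last available lead-in samples, analysed at the same central laboratory, and the drug-screen exclusion needs verification by repeat testing. This is right too. The comparison supports adding an exclusion line; it does not show that other results hold back the first dose.

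The lead-in protocols may already exclude breast-feeding women and withdraw women found pregnant. That cannot be checked. It narrows the group mainly to pregnancies first detectable at the final lead-in visit, and it may close the breast-feeding gap altogether. Women who received Lu AF35700 in the lead-in have already been exposed, so wholly new exposure concerns the comparator arms. Section 1.1.4 regards no nonclinical effect other than ECG changes as relevant to humans, so the documents state no specific foetal hazard. Finally, the 300 planned patients include men and women who cannot conceive.

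These points limit the size of the problem. None supplies the missing entry rule.

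**Conclusion.** The concern holds. The explicit exclusion is in 1 of 3 lists, and no provision makes a positive result exclusionary or requires a negative one before a roll-over woman's first dose. Followed literally, the plan can start Lu AF35700 in a woman already pregnant at Baseline, a condition for which it would then have to stop treatment.

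The conclusion rests on the text alone. The practical consequence depends on two things that the documents do not give: the laboratory turnaround and the lead-in entry and withdrawal rules. No affected patient is shown. This is a patient-safety correction that should be made; it does not bear on the validity of the analyses.

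**What to change.** Add Other Patients criterion 5 to the 16159A and 16323A exclusion lists in section 5.3. In Panel 2, footnote q or u, state that women of childbearing potential must have a negative pregnancy result before the first dose of Lu AF35700. A urine dipstick at Baseline is enough. Panel 4 already provides for it and already requires serum confirmation of a positive; the first dose should wait for that confirmation.

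The cost is one line in each of two lists, one footnote sentence, and one dipstick per woman of childbearing potential. A urine sample is expected at Baseline anyway for the drug screen. The downside is that an occasional roll-over patient is delayed or not enrolled.

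If enrolment has closed, as the SAP's account suggests, the sponsor can still check the linked Baseline pregnancy results of roll-over women and correct the wording for later extension studies.
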